## 6.2. Imaging Results

Certain parameters obtained from OCT assessments will be evaluated by 2 or 3 image readers interpreting the same image. For such parameters, two readers provide their assessments initially. If their assessments do not agree to a certain degree, a third reader provides an additional evaluation. For the purposes of statistical summaries, in the case of numerical measurements, a median value across the readers will be used. In the case of categorical parameters, a category provided by majority (two readers) will be used.

OCT measurements may be obtained post-surgery on study day 1 and/or on follow-up study day 2 to assist in surgery training purposes. These data will not be included in statistical summaries or analyses but will be included in any subject data listings provided.

Descriptive statistics will be presented for OCT CST, total area of GA by FAF in mm^2, and square root of total area of GA by FAF in mm, at baseline and at each scheduled follow-up time point and for the change from baseline, for the treated and fellow eye.

The yearly rate of change in GA area at an assessment is calculated as the change from baseline in the square root of total area of GA by FAF in mm, divided by the number of days of follow-up for that assessment, multiplied by 365. The number of days of follow-up for a given assessment time point is calculated as that visit date – surgery date + 1. This measurement will be summarized using descriptive statistics at the 3-, 6- and 12-month follow-up time points for the fellow eye, and at the 3- and 12-month follow-up time points for the fellow eye. Note for the fellow eye, scans are only read by the central reader for a subset of time points.

Imaging data for individual subjects will be presented in a data listing.

The microperimetry and specialized OCT image analysis data will be examined by expert specialty laboratory reviewers. Analysis of microperimetry data is beyond the scope of this document and no statistical tables are planned for this effort.

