The overall reason for the amendment: to include modifications to inclusion and exclusion criteria taken from learning acquired through the first 21 subjects (the initial Safety Cohort), to include a 2nd Safety Cohort of 21 additional subjects agreed upon by the DSMB, to expand the screening to treatment window to 45 days and to include additional baseline assessments (axial length). Other modifications are included to provide clarity to study sites where there was ambiguity, or the protocol was silent on logistical issues that have arisen. Editorial changes were made to improve the overall clarity of the Protocol.

Applicable Section(s)	Description of Change(s)
Overview of Study Design	Updated the target number of subjects to be enrolled in the study to “approximately 285 subjects”. Specified the screening period of up to 45 days before initial randomization that subjects must be confirmed with a diagnosis of GA of the macular secondary to age-related macular degeneration with associated vision loss. Clarified vision between the patient’s eyes as “not clinically equal” or “ clinically equal” for the relevant disease state of the eyes. Updated the approximate number of subjects to 75 in the Safety Run-in Phase of the study. Specified the addition of the 2 nd Safety Cohort. Also updated the number of sites for this phase of the study to 20.
Screening Phase	Clarified that subjects may have the option to donate their eyes for histological evaluation post mortem. Specified the screening period of up to 45 days between a subject giving written informed consent and occurrence of treatment. Also clarified that screening activities need not take place in one visit. Clarified that the BCVA examination to determine eligibility should be performed prior to any other ocular study procedures that might interfere with vision assessments (dilation, bright light examination, etc). Also specified that axial length will be recorded at baseline. Indocyanin green angiography will be performed for all subjects unless discussed with the Sponsor
Safety Run-in Phase	Clarified that a minimum of the first 3 eligible subjects at each center will receive active treatment in an uncontrolled, open-label Safety Run-in Phase. Clarified that the first 21 subjects at 8 (not 7) study sites will comprise the initial Safety Cohort, and specified the addition of the 2 nd Safety Cohort

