Ocular TEAEs will be summarized by treatment group and preferred term according to MedDRA terminology, as well as by affected eyes (events occurring in the treated eye only, in the fellow eye only, and in both eyes).

The number and percentage of subjects who experienced at least 1 treatment-emergent serious AE (SAE) will be presented in summary tables by treatment group and preferred term, as well as by preferred term within system-organ class according to MedDRA terminology.

The number and percentage of subjects who experienced at least 1 treatment-emergent AE will be presented in summary tables by treatment group and preferred term, as well as by preferred term within system-organ class according to MedDRA terminology.

Data regarding the Delivery System and surgical procedure will be tabulated by treatment group. A listing of all data pertaining to the Delivery System and surgical procedure, as well as any surgical deviations and surgical medications, will be provided. Adverse events for subjects who receive surgery but not CNTO 2476 cells will be listed.

TIME AND EVENTS SCHEDULES

Table 1: Schedule of Study Assessments for the Safety Run-in Phase and the Randomized Double-masked Treatment Phase from Screening through the Month 12 Postoperative Visit

	Optional Pre-Screening	Screen (see note)	Treatment Day 1 (pre-op)	Day 2	Days 7 & 15 (±3d)	Week 4 (±3d)	Month 2 (±3d)	Month 3 (±3d)	Month 6 (±3d)	Month 12 (±7d)
Visit number		1	2	3	4, 5	6	7	8	9	10
Informed consent	x ^a	x								
Inclusion/Exclusion criteria		x								
Medical History and demographics		x								
Vital signs		x	x	x	x	x	x	x	x	x
Physical exam		x								x
Best Corrected Visual Acuity (BCVA)	x	x ^b				x	x	x	x	x
Low Luminance Visual Acuity		x				x	x	x	x	x
Axial Length		x ^c								
Contrast sensitivity		x						x	x	x
MN Read		x						x	x	x
IOP		x		x	x	x	x	x	x	x
Slit lamp biomicroscopy/ophthalmoscopy		x		x	x	x	x	x	x	x
Microperimetry assessments		x						x	x	x
Fundus photography		x			x	x	x	x	x	x
SD-OCT ^d		x			x	x	x	x	x	x
Fundus autofluorescence		x			x	x	x	x	x	x
Fluorescein angiography	x							x		x
Indocyanin green angiography	x									
Routine laboratory ^e		x				x				x
Routine urinalysis		x				x				x
Blood samples for immunogenicity ^f		x			x	x	x	x	x	x
Medication History		x	x							
NEI-VFQ-25, SF-36 ^l , and Near Vision Subscale (3-item), FRI		x							x	x
Randomization (for the Double-masked Treatment Phase only) ^g										
CNTO 2476 Administration			x ^h							
PGIC-S								x	x	

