PGIC-Q								x	x	
CGIC								x	x	
Change in concomitant medications				<-----	Continuous----->					
Adverse events				<-----	Continuous----->					
Blood samples volume ⁱ		16.3 mL	0	0	20 mL ^k	16.3mL	10 mL	10 mL	10 mL	16.3 mL

BCVA=Best Corrected Visual Acuity; CGIC=Clinician Global Impression of Change; ETDRS=Early Treatment Diabetic Retinopathy Study; IOP=intraocular pressure; MN Read=Minnesota reading test; NEI-VFQ-25=National Eye Institute Visual Functioning Questionnaire; PGIC-Q=Patient Global Impression of Change – Quality of Life; PGIC-S=Patient Global Impression of Change – Symptoms; SD-OCT=spectral domain optical coherence tomography; SF-36=Short Form (36) Health Survey, FRI= Functional Reading Index questionnaire

Note 1: Screening procedures must occur within 45 days prior to treatment and may occur over multiple days. An additional optional pre-screening visit may be performed to determine potential subject BCVA for eligibility purposes. At the next screening visits, BCVA will be performed twice and the best value (lowest logMAR value) will be used as the subjects' baseline BCVA value.

Note 2: If a subject withdraws early from the Safety Run-in Phase, the end-of-study assessments (described in [Table 2](#)) should be performed.

- a) Subjects will be presented with an optional pre-screening ICF to allow the determination of their BCVA results prior to full study screening. The subjects who meet the BCVA eligibility criteria will be further screened to determine the full study eligibility. For the full study eligibility assessments, the subject will be presented a separate ICF within 45 days prior to treatment. The pre-screening visit is optional
- b) Best Corrected Visual Acuity testing includes BCVA using the ETDRS chart under high illumination and standardized conditions at 4 meters and 1 meter (as needed).
- c) Axial length should be recorded once at screening as a baseline measure. Any instrument may be used OR measurement taken from the subjects medical records may be utilized. Measurement, instrument and date of recording will be noted in the CRF.

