4.1. Inclusion Criteria

Each potential subject must satisfy all of the following criteria to be enrolled in the study.

1. Subject must be a man or woman at least 55 years to 90 years of age, inclusive.
- 2.2 Diagnosis of GA secondary to AMD confirmed within 45 days prior to initial randomization. Diagnosis verified by the central reading center using fundus photographs and including the following;

- The study eyes must have at least 1 GA lesion that involves the fovea, and a Macular Photocoagulation Study (MPS) disc areas (DA) of ≥ 0.5 and ≤ 7 (1 MPS disc area equivalent to 2.54 mm^2 on the retina) determined by screening images of fundus autofluorescence photographs as calculated by the reading center. If GA is multifocal, at least 1 lesion must be ≥ 0.5 DA.
 - In the Safety Run-in Phase only, DA of ≥ 0.5 with no maximum specified area, as long as the criteria below for photography can be met and the surgeon determines that the GA size will not impede cell delivery.
- Geographic atrophy must be able to be photographed in its entirety and may be contiguous with peripapillary atrophy.
- Retinal photographs, fundus autofluorescence images, and angiography of sufficient quality, allowing assessment of the macular area according to standard clinical practice, can be obtained.
- The imaging center must be able to delineate and confirm peripapillary atrophy with fundus photography and fundus autofluorescence.
- Images must include the central field 1, 2, and 3 field images as defined by the University of Wisconsin standards as well as a supero-temporal image to capture the subretinal injection area if possible.

- 3.2 Study eyes will have a BCVA of 20/80 to 20/800 (ETDRS logMAR value 0.6-1.6). The treatment eye will be that with the worse BCVA at screening. If BCVA is clinically equivalent, the eye with the larger GA determines the study eye.
4. Subject is a suitable candidate for ophthalmologic surgery, is willing and able to comply with the surgical procedure, scheduled visits, treatment plan, laboratory tests and other study procedures. Subject has met criteria of the surgery center anti-coagulation protocol, if applicable.
5. Female subjects must be post-menopausal with last menses 12 months prior, or longer, OR a measured follicle stimulating hormone $\geq 26 \text{ mIU/mL}$.

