## 2.2. Baseline

For all assessments except for BCVA measurements (i.e., logMAR and total letters correct, both standard and low luminance), baseline will be defined as the most recent value prior to the Surgery Date (and time, if applicable). Thus the baseline could be derived based on Screening or Day 1 pre-op assessments or unscheduled pre-op assessments where applicable.

Baseline BCVA is assessed at an optional pre-screening visit (not recorded on the electronic case report form [eCRF] thus not used for analysis) and at the regular Screening visit (twice at that visit). For BCVA logMAR and total letters correct (both standard and low luminance), the better score at these 2 assessments will be used for baseline. For BCVA logMAR, a lower score is better. For total letters correct, a higher value is better.

Re-screening is allowed per protocol and the subject is not necessarily required to repeat every test during the 2nd screening. When a subject is re-screened, he/she receives a new subject ID. If a baseline value is not present for the current subject ID for this type of subject, it will be necessary to use the screening/baseline value captured in the 1st screening visit for that subject (captured using their previous subject ID) as the baseline value.

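### The yearly GA growth rate divides change since the pre-operative image by days since surgery, so under constant growth it is overstated, most at the earliest visits

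*SAP*

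**What the plan says.** - **Rate formula (SAP 6.2).** The yearly rate is the "change from baseline in the square root of total area of GA by FAF in mm, divided by the number of days of follow-up", multiplied by 365. The divisor is then defined: "The number of days of follow-up for a given assessment time point is calculated as that visit date – surgery date + 1". The rate is summarised at Months 3, 6 and 12 for one eye and at Months 3 and 12 for the other.
- **Baseline (SAP 2.2).** For every assessment except BCVA, baseline is the last value before surgery. "Thus the baseline could be derived based on Screening or Day 1 pre-op assessments or unscheduled pre-op assessments where applicable". A re-screened subject may carry over a value recorded under the earlier subject ID.
- **When FAF is taken before surgery (Protocol Table 1).** The row "Fundus autofluorescence" is marked at Screening, blank on Treatment Day 1 and Day 2, and next marked at Days 7 and 15. Criterion 2.2 in Protocol 4.1 likewise has the lesion area "determined by screening images of fundus autofluorescence photographs as calculated by the reading center".
- **Length of the gap.** Note 1 to Protocol Table 1: "Screening procedures must occur within 45 days prior to treatment and may occur over multiple days". The Amendment 2 summary gives as one of its purposes "to expand the screening to treatment window to 45 days".
- **Status of the measure.** Protocol 9.2.2 lists GA growth rate from baseline to 6 and 12 months as a major secondary endpoint.

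**The concern.** A growth rate needs a change and the time over which that change accrued. Here the change normally starts at the Screening image and the time starts at surgery. Growth in the days between the two is counted, but those days are not. Neither document adjusts for this.

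If lesions grow at about the same pace before and after surgery, every tabulated rate is too high. The relative error shrinks as follow-up lengthens, so a constant rate would appear to decline from Month 3 to Month 12. In a single-arm cell-therapy study that pattern could be misread as growth slowing after treatment.

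**Working it through.** The documents state no GA growth figure, so there is none to reproduce. The check is algebra plus a range for the unknown gap.

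**Inputs**
- g = days from baseline FAF image to surgery. Not given, so assumed: 7, 14, 30 and 45 days. Forty-five is the ordinary screening limit in Table 1, Note 1.
- d = days from surgery to visit. Nominal values: 91 (Month 3), 182 (Month 6), 365 (Month 12).
- r0, r1 = growth per day before and after surgery on the square-root scale; k = r0/r1.

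**Formulas**
- Measured change = g·r0 + d·r1
- SAP rate = change/(d+1)
- Interval-matched rate = change/(g+d)
- Ratio of the two = (g+d)/(d+1), whatever k is

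With k = 1 the matched rate is the true rate, so the ratio is also the overstatement factor.

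| g | Month 3 (d=91) | Month 6 (d=182) | Month 12 (d=365) |
|---|---|---|---|
| 7 | 98/92 = 1.065 | 189/183 = 1.033 | 372/366 = 1.016 |
| 14 | 105/92 = 1.141 | 196/183 = 1.071 | 379/366 = 1.036 |
| 30 | 121/92 = 1.315 | 212/183 = 1.158 | 395/366 = 1.079 |
| 45 | 136/92 = 1.478 | 227/183 = 1.240 | 410/366 = 1.120 |

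At g = 1 the factor is exactly 1. At g = 0 the added day makes the rate slightly low: 1.1%, 0.5% and 0.3% at Months 3, 6 and 12. The overstatement therefore needs g > 1.

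**Apparent slowing of a constant rate**, as 1 minus the ratio of the later factor to the earlier one:
- Month 6 to Month 12: 1.6%, 3.3%, 6.8% and 9.7% for g = 7, 14, 30 and 45.
- Month 3 to Month 12: about 9%, 18% and 24% for g = 14, 30 and 45.

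**Visit windows barely matter.** At g = 14, Month 6 ± 3 days gives 1.070 to 1.072, and Month 12 ± 7 days gives 1.035 to 1.036.

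**If growth changes at surgery.** Error against the post-operative rate r1 at Month 6, where the SAP formula gives (g·k+d)/(d+1) and the matched divisor gives (g·k+d)/(g+d):

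| g | k | SAP formula | Matched divisor |
|---|---|---|---|
| 14 | 0.5 | +3.3% | −3.6% |
| 14 | 1.33 | +9.7% | +2.4% |
| 45 | 0 | −0.5% | −19.8% |
| 45 | 0.5 | +11.7% | −9.9% |
| 45 | 1.33 | +32.2% | +6.6% |

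The two errors are equal in size when g·k + d = 2(d+1)(g+d)/[(d+1)+(g+d)]. For g = 14, d = 182 this is 2·183·196/379 = 189.28, so k = 7.28/14 = 0.52. Over g = 14 to 45 at Months 6 and 12, the break-even k runs from 0.46 to 0.53.

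**The case against.** The strongest reply is that the endpoint concerns growth after treatment, that visits are timed from treatment, and that SAP 2.1 sets Day 1 at surgery. On that reading the last pre-operative image merely stands in for the lesion at time zero, and the formula is an approximation. That explains the divisor but does not rescue it: the formula keeps pre-operative growth and discards pre-operative time, so it does not isolate the post-operative rate either. It comes closer to that rate than the matched divisor only if pre-operative growth was below about half of post-operative growth, and no document reports such a change.

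These points stand as limits:
- **The large figures may apply to no analysed subject.** The analysis set is the first 21 subjects (SAP 2.5). The 45-day window came with Amendment 2, which drew on experience with those same subjects, and no one is enrolled under Amendment 3 (Protocol 11.6). The earlier window's length is not given. The rule letting re-screened subjects reuse images from the previous 60 days came with the same amendment, so gaps beyond 45 days are not carried through here. A Day 1 or unscheduled pre-operative image would shorten the gap further.
- **Constant growth is an assumption.** The procedure itself causes a small retinal detachment (Protocol 12.1.1), and the documents give no growth rates.
- **Both eyes share the formula.** With the same image dates the treated-to-fellow ratio is unchanged, and false slowing would also show in the untreated eye. The rates themselves, and any absolute difference between eyes, are still inflated.
- **The stakes are limited.** Development has stopped, analysis is descriptive, no decision rule uses the rate, and no between-eye difference or trend analysis is planned. Area, square-root area and change from baseline are tabulated separately and are unaffected; individual imaging data are listed.

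**Conclusion.** The concern holds. The divisor in SAP 6.2 does not match the change it divides, and that follows from the SAP's own definitions read with Protocol Table 1. The factor (g+d)/(d+1) between the SAP rate and the imaged-interval average needs no assumption about growth. Calling it an overstatement of the true rate requires roughly constant growth across surgery and g > 1.

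For gaps of 7 to 14 days the overstatement is 3.3% to 7.1% at Month 6 and 1.6% to 3.6% at Month 12. It is about twice the Month 6 figure at Month 3, which the SAP also tabulates. The 45-day figures mark the ordinary limit of the current text and are not an estimate. The realised size is unknown and may be small. Impact is minor to moderate, but a major secondary endpoint should not be reported with a formula that is wrong as written when the correction is this cheap.

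**What to change.** In SAP 6.2:
1. For both eyes, define days of follow-up as the follow-up FAF image date minus the baseline FAF image date.
2. Where a re-screened subject's baseline comes from the earlier subject ID, carry that image's date along with its value.
3. Report the median and range of days from baseline FAF image to surgery.
4. State in the SAP and the report that the rate is an average over the imaged interval, including its pre-operative part, and so dilutes any change in growth that begins at surgery.
5. Correct a drafting slip in the same paragraph, which adds no weight to this point: both lists of time points are assigned to the fellow eye. The sentence that follows shows that the first list (Months 3, 6 and 12) is meant for the treated eye.

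The cost is a few sentences and one derived variable, built from assessment dates that SAP 2.1 already uses. The new divisor includes some pre-operative time. Its share, g/(g+d), is 14/196 = 7.1% at g = 14 and 45/227 = 19.8% at g = 45 for Month 6, and 3.7% and 11.0% for Month 12. Items 3 and 4 make that visible to the reader.

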- d) Includes routine hematology (hemoglobin, hematocrit, red blood cell count, white blood cell count with differential, platelet count, prothrombin time, and partial thromboplastin time) and serum chemistry (sodium, potassium, chloride, blood urea nitrogen, creatinine, glucose, aspartate aminotransferase, alanine aminotransferase, gamma-glutamyltransferase, total bilirubin, alkaline phosphatase, lactic acid dehydrogenase, uric acid, calcium, albumin, and total protein) and urinalysis (dipstick).
- e) Optional blood draw (ie, for subjects who provide consent for this blood draw)
- f) Includes samples for antibody assay testing.
- g) Enrollment and randomization of subjects in the Double-masked Treatment Phase was to follow the DSMB's evaluation of the Safety Run-in Phase and its supportive recommendation to advance the study to the Double-masked Treatment Phase. However, the Double-masked Treatment Phase has been eliminated from this study protocol.
- h) Includes assessment of Delivery System.
- i) SF-36 is included to assess the measurement properties of the NEI-VFQ-25 and Near Vision subscale.
- j) Blood sample estimates based upon the following volumes per sample: Screening=16.3 mL, DNA=8.5 mL, Day 7=10 mL, Day 15=10 mL, Week 4=16.3 mL, Month 2=10 mL, Month 3=10 mL, Month 6=10 mL, Month 12=16.3 mL Total volume of blood through Month 12 = approximately 107.4 mL.
- k) Includes 10 mL samples each for Day 7 and Day 15
- l) Optional SD-OCT at day 1 (post-operatively) and day 2 may be performed

Table 2 Schedule of Study Assessments During the Long-term Follow-up Phase*

	Time Post-treatment			
	Month 18 (± 2 wk)	Month 24 (± 2 wk)	Month 30 (± 2 wk)	Month 36 (± 2 wk)
Visit number	11	12	13	14
Best Corrected Visual Acuity testing	x	x	x	x
IOP	x	x	x	x
Slit lamp biomicroscopy / ophthalmoscopy	x	x	x	x
SD-OCT	x	x	x	x
Fundus photography	x	x	x	x
Fundus autofluorescence	x	x	x	x
Concomitant medications	<-----Continuous----->			
Adverse events ^b	<-----Continuous----->			

Footnotes

* After the 12-month acute phase of the study subjects will be followed for 2 years. Subjects will come in for a follow-up visit every 6 months.

AE=adverse event; IOP=intraocular pressure; SAE=serious adverse event; SD-OCT=spectral-domain optical coherence tomography.

a) If a subject is withdrawn from the study, he/she will be asked to have the End-Of-Study Visit assessments performed.

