9.2.2. Endpoints

Primary Endpoints

The endpoints of the open-label Safety Run-in Phase are all related to the objective of evaluating the safety profile of the procedure, Delivery System, and of the implanted hUTC cells.

Major Secondary Endpoints

- Proportion of subjects losing ≥ 15 BCVA letters from baseline at 12 months following treatment with CNTO 2476
- Change in mean number of BCVA letters from baseline at the 6- and 12-month visits following treatment with CNTO 2476
- Growth rate of GA lesion documented at baseline to 6 and 12 months following treatment with CNTO 2476. The area of GA is determined based primarily on fundus autofluorescence as well as fluorescein angiography and fundus photos

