#### **Major Secondary Objectives**

The major secondary objectives of this study are the following:

- to assess the safety and performance profile of the Delivery System, the safety and tolerability of the suprachoroidal surgical approach, and the safety and tolerability of CNTO 2476 cells in the open-label Safety Run-in Phase
- to assess the effects of CNTO 2476 on anatomic correlates of treatment, including change in the area of geographic atrophy (GA)
- to assess the effects of CNTO 2476 on additional and alternative efficacy outcomes including duration of clinical response.

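### SAP 6.2 assigns both visit lists for the yearly GA growth rate to the fellow eye, so as written the rate is not summarised for the treated eye

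*SAP*

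**What the plan says.** **Endpoint.** Protocol section 9.2.2 includes among the major secondary endpoints: "Growth rate of GA lesion documented at baseline to 6 and 12 months following treatment with CNTO 2476". Area is to be judged mainly from fundus autofluorescence (FAF). Protocol section 9.2.1.2 describes the same measure to 12 months. Neither section gives a formula.

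**Formula.** SAP section 6.2 supplies one. The yearly rate is the "change from baseline in the square root of total area of GA by FAF in mm, divided by the number of days of follow-up", multiplied by 365. Days are counted from surgery, plus one.

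**Schedule.** After naming Month 3, the same section gives the remaining visits as "6- and 12-month follow-up time points for the fellow eye, and at the 3- and 12-month follow-up time points for the fellow eye". The sentence after that one reads: "Note for the fellow eye, scans are only read by the central reader for a subset of time points".

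**Related summaries.** The paragraph before the formula plans descriptive statistics for GA area, square-root GA area and their changes from baseline, for both eyes, at baseline and every scheduled follow-up visit. Individual imaging data are to be listed.

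**Imaging visits.** Protocol Table 1 schedules FAF at screening and at visits up to Month 12. Table 2 schedules it at Months 18, 24, 30 and 36.

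**The concern.** The protocol names the endpoint but does not say how to compute it, so SAP 6.2 is what turns it into a number. SAP section 2 makes treated eye and fellow eye the reporting labels, so the label in the scheduling sentence decides what is programmed. The other eye-level efficacy summaries in SAP sections 6.1 to 6.4 name both eyes. This sentence names only one, twice.

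A programmer who follows it would produce a growth-rate table for the untreated eye alone. There is no control group (Protocol section 3.2.1), so the fellow eye is the only reference within the study. A table confined to it would leave that reference with nothing to be compared against. The sentence also leaves open whether a Month 6 rate is expected for the fellow eye.

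**Working it through.** The plan states no figure to reproduce. The check is a comparison of texts, plus one small calculation.

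**Step 1. Which eye at which visit.**

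| Yearly rate | Treated eye | Fellow eye |
|---|---|---|
| Protocol 9.2.2 endpoint visits | 6, 12 (the eye given CNTO 2476) | not specified |
| SAP 6.2 as written, first list | none | 3, 6, 12 |
| SAP 6.2 as written, second list | none | 3, 12 |
| SAP 6.2 with one word changed | 3, 6, 12 | 3, 12 |

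As written, 0 of the 2 endpoint visits are covered for the treated eye, and the two fellow-eye lists conflict on Month 6. With the first list moved to the treated eye, both endpoint visits are covered and the conflict disappears.

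**Step 2. Which list was meant for which eye.** The sentence that follows gives a reason for the fellow eye to have fewer visits: its scans are not all read. The second list is the shorter one, so it fits the fellow eye, and the first list is left for the treated eye. No other sentence in section 6.2 points the other way.

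**Step 3. How far the planned treated-eye change stands in for the rate.** By the SAP formula, rate = change in square-root area × 365 / (days since surgery + 1). The multiplier shows how the tabulated change relates to the rate. I assume nominal visits at 182 and 365 days after surgery, with the windows in Protocol Table 1 (±3 and ±7 days).

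- Month 12: 365/(358 + 1) = 1.017; 365/(365 + 1) = 0.997; 365/(372 + 1) = 0.979.
- Month 6: 365/(179 + 1) = 2.03; 365/(182 + 1) = 1.99; 365/(185 + 1) = 1.96.

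Protocol section 9.1.1 gives the Month 6 window in business days. If three business days span up to five calendar days, the limits are 365/178 = 2.05 and 365/188 = 1.94, which does not alter the picture.

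Within the windows, the planned Month 12 change is therefore within about 2% of the yearly rate. The planned Month 6 change is about half of it.

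**Step 4. Whether the Month 12 stop matters.** The last rate visit in SAP 6.2 is Month 12. The last endpoint visit in Protocol 9.2.2 is also Month 12. No endpoint visit is omitted by stopping there.

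**The case against.** The strongest reply is that this is an evident typing slip with little consequence. The note on fellow-eye reads shows what was intended. Treated-eye GA area, square-root area and change are tabulated at every scheduled visit, and the data are listed. The study is small, single-arm and descriptive, its primary objective is the safety and performance of the surgical approach and Delivery System, and the development programme has been discontinued. No decision rule depends on this table.

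Most of that stands, and it limits the size of the point. It does not remove it. A likely intention is not a specification, and whoever programs or checks the tables should not have to infer which eye carries a protocol endpoint. At Month 6 the tabulated change also differs from the rate by a factor of about two.

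Three stronger readings are tempting, and the documents do not support them.

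- *Treated-eye growth will go unreported.* Only the annualised summary is missing. The unannualised change is planned, and the SAP objective on change in GA area is served by it.
- *The treated eye was left out on purpose.* The note on fellow-eye reads points to a slip.
- *Stopping at Month 12 while FAF runs to Month 36 is an error, or contributes to the gap.* The protocol defines the endpoint at 6 and 12 months, and the mislabelled eye has nothing to do with the stopping point. One can argue that later rates are less noisy: if reading error were constant and independent, the error SD of an annualised rate would fall as 1/T, in the ratio 4 : 1 : 0.33 at 3, 12 and 36 months. The documents give no reading error, and the ratio ignores attrition and differences between subjects in true growth. It bears only on whether an extra summary would be useful.

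**Conclusion.** The scheduling sentence in SAP 6.2 is wrong as written and should be corrected. Read literally, it yields no treated-eye summary of the yearly GA rate at Month 6 or Month 12, and it contradicts itself on Month 6 for the fellow eye.

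The consequence is confined to that one annualised summary. The rate could be derived from planned tables and listings: almost directly at Month 12, and after roughly doubling at Month 6. Those two statements rest on the nominal visit days and windows used above. That the first list belongs to the treated eye is an inference from the note on fellow-eye reads, and a strong one. The absence of rates at Months 18 to 36 is not an error.

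**What to change.** In the scheduling sentence of SAP 6.2, change the first *fellow eye* to *treated eye*. The yearly rate is then summarised at Months 3, 6 and 12 for the treated eye and at Months 3 and 12 for the fellow eye. Before finalising, the sponsor should confirm with the reading center that the fellow-eye list matches the visits actually read.

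The cost is one word in the SAP. No new scans or reads are needed for the treated eye, because its GA area is already to be summarised at these visits.

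Optionally, add descriptive treated-eye rates at Months 18, 24, 30 and 36, and fellow-eye rates at any of those visits where scans were read. That means extra columns in the same table.
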